14.2 Study Records Retention

Study documents will be retained for the longer of 3 years after close-out, 5 years after final reporting/publication, or 2 years after the last approval of a marketing application is approved for the drug for the indication for which it is being investigated or 2 years after the investigation is discontinued and FDA is notified if no application is to be filed or if the application has not been approved for such indication. No records will be destroyed without the written consent of the

CONFIDENTIAL

This material is the property of the NYU School of Medicine and Langone Medical Center. Do not disclose or use except as authorized in writing by the study sponsor
Interventional Template Version: 11 January 2019

sponsor, if applicable. It is the responsibility of the sponsor to inform the investigator when these documents no longer need to be retained.

14.3 Protocol Deviations

A protocol deviation is any noncompliance with the clinical trial protocol, GCP, or Manual of Procedures (MOP) requirements. The noncompliance may be either on the part of the participant, the investigator, or the study site staff. As a result of deviations, corrective actions are to be developed by the site and implemented promptly.

These practices are consistent with ICH E6:

- 4.5 Compliance with Protocol, sections 4.5.1, 4.5.2, and 4.5.3
- 5.1 Quality Assurance and Quality Control, section 5.1.1
- 5.20 Noncompliance, sections 5.20.1, and 5.20.2.

It is the responsibility of the site PI/study staff to use continuous vigilance to identify and report deviations within 7 working days of identification of the protocol deviation, or within 7 working days of the scheduled protocol-required activity.

Protocol deviations must be reported to the local IRB per their guidelines. The site PI/study staff is responsible for knowing and adhering to their IRB requirements. Further details about the handling of protocol deviations will be included in the MOP.

14.4 Publication and Data Sharing Policy

This study will comply with the NIH Public Access Policy, which ensures that the public has access to the published results of NIH funded research. It requires scientists to submit final peer-reviewed journal manuscripts that arise from NIH funds to the digital archive PubMed Central upon acceptance for publication.

The International Committee of Medical Journal Editors (ICMJE) member journals have adopted a clinical trials registration policy as a condition for publication. The ICMJE defines a clinical trial as any research project that prospectively assigns human subjects to intervention or concurrent comparison or control groups to study the cause-and-effect relationship between a medical intervention and a health outcome. Medical interventions include drugs, surgical procedures, devices, behavioral treatments, process-of-care changes, and the like. Health outcomes include any biomedical or health-related measures obtained in patients or participants, including pharmacokinetic measures and AE. The ICMJE policy, and the Section 801 of the Food and Drug Administration Amendments Act of 2007, requires that all clinical trials be registered in a public trials registry such as ClinicalTrials.gov, which is sponsored by the National Library of Medicine. Other biomedical journals are considering adopting similar policies. For interventional clinical trials performed under NIH IC grants and cooperative agreements, it is the grantee's responsibility to register the trial in an acceptable registry, so the research results may be considered for publication in ICMJE member journals. The ICMJE does not review specific studies to determine whether registration is necessary; instead, the committee recommends that researchers who have questions about the need to register err on the side of registration or consult the editorial office of the journal in which they wish to publish.

CONFIDENTIAL

This material is the property of the NYU School of Medicine and Langone Medical Center. Do not disclose or use except as authorized in writing by the study sponsor
Interventional Template Version: 11 January 2019

FDAAA mandates that a "responsible party" (i.e., the sponsor or designated principal investigator) register and report results of certain "applicable clinical trials":

- Trials of Drugs and Biologics: Controlled, clinical investigations, other than Phase I investigations of a product subject to FDA regulation;
- Trials of Devices: Controlled trials with health outcomes of a product subject to FDA regulation (other than small feasibility studies) and pediatric postmarket surveillance studies.
- NIH grantees must take specific steps to ensure compliance with NIH implementation of FDAAA.

15 Study Finances

15.1 Funding Source

This study is financed by JDS therapeutics.

15.2 Costs to the Participant

All office visits, tests and treatment drugs for the trial will be provided to the patient free of cost. However, the patient will not be compensated for participating in the study, nor will reimbursement be provided for travel costs to the office.

16 Study Administration

16.1 Study Leadership

The Steering Committee will govern the conduct of the study. The Steering Committee will be composed of the Study Chairman, the PI of the Coordinating Center, the PI of the clinical sites, chairperson of the Study Coordinators subcommittee, and the PI of the Central Biochemistry Laboratory. The Steering Committee will meet in person at least annually.

17 Conflict of Interest Policy

The independence of this study from any actual or perceived influence, such as by the pharmaceutical industry, is critical. Therefore any actual conflict of interest of persons who have a role in the design, conduct, analysis, publication, or any aspect of this trial will be disclosed and managed. Furthermore, persons who have a perceived conflict of interest will be required to have such conflicts managed in a way that is appropriate to their participation in the trial. The study leadership has established policies and procedures for all study group members to disclose all conflicts of interest and will establish a mechanism for the management of all reported dualities of interest.

Any investigator who has a conflict of interest with this study (patent ownership, royalties, or financial gain greater than the minimum allowable by their institution, etc.) must have the conflict reviewed by the NYU Langone Conflict of Interest Management Unit (CIMU) with a Committee-sanctioned conflict management plan that has been reviewed and approved by the study sponsor prior to participation in this study. All NYULMC investigators will follow the applicable conflict of interest policies.

CONFIDENTIAL

This material is the property of the NYU School of Medicine and Langone Medical Center. Do not disclose or use except as authorized in writing by the study sponsor
Interventional Template Version: 11 January 2019

18 References

1. Portman, David J., Margery LS Gass, and Vulvovaginal Atrophy Terminology Consensus Conference Panel. "Genitourinary syndrome of menopause: new terminology for vulvovaginal atrophy from the International Society for the Study of Women's Sexual Health and the North American Menopause Society." *Climacteric* 17.5 (2014): 557-563.
2. Gandhi, Jason, et al. "Genitourinary syndrome of menopause: an overview of clinical manifestations, pathophysiology, etiology, evaluation, and management." *American journal of obstetrics and gynecology* 215.6 (2016): 704-711.

27. National Research Council. The prevention and treatment of missing data in clinical trials. National Academies Press, 2010.

CONFIDENTIAL

This material is the property of the NYU School of Medicine and Langone Medical Center. Do not disclose or use except as authorized in writing by the study sponsor
Interventional Template Version: 11 January 2019

19 Attachments

19a The Vulvovaginal Symptom Questionnaire

The Vulvovaginal Symptom Questionnaire

The following questions were developed to assess skin symptoms of women. The skin surrounding the vagina is called the vulva. Just like skin in other parts of the body, the vulva can sometimes become irritated. Many women experience discomfort in the region of the vulva. These symptoms may be mild, but can sometimes be severe. The following questions will ask you about your vulvar skin symptoms during the past week.

During the past week, have you been bothered by:

1. Your vulva itching? No Yes
2. Your vulva burning or stinging? No Yes
3. Your vulva hurting? No Yes
4. Your vulva being irritated? No Yes
5. Your vulva being dry? No Yes
6. Discharge from your vulva or vagina? No Yes
7. Odor from your vulva or vagina? No Yes
8. Worry about your vulvar symptoms?
(for example, that it will spread, get worse, scar, etc.) No Yes
9. The appearance of your vulva? No Yes
10. Frustration about your vulvar symptoms? No Yes
11. Embarrassment about your vulvar symptoms? No Yes
12. The effects of your vulvar symptoms on your interactions with others? No Yes
13. The effects of your vulvar symptoms on your desire to be with people? No Yes
14. Your vulvar symptoms making it hard to show affection? No Yes
15. The effects of your vulvar symptoms on your daily activities? No Yes
16. Your vulvar symptoms affecting your desire to be intimate? No Yes
17. Are you currently sexually active with a partner?
 No → Thank you. You are done with this questionnaire.
 Yes → Please proceed with the next 4 questions
18. The effects of your vulvar symptoms on your sexual relationships? No Yes
19. Your vulvar symptoms causing pain during sexual activity? No Yes
20. Your vulvar symptoms causing dryness during sexual activity? No Yes
21. Your vulvar symptoms causing bleeding during sexual activity? No Yes

CONFIDENTIAL

This material is the property of the NYU School of Medicine and Langone Medical Center. Do not disclose or use except as authorized in writing by the study sponsor
Interventional Template Version: 11 January 2019

19b Revaree Package Insert

(HYALURONIC ACID SODIUM SALT 0.25%)

Vaginal suppositories

For intravaginal use only

PRODUCT DESCRIPTION

PRODUCT DESCRIPTION
REVAREE vaginal suppositories are semi-solid, off-white suppositories for intravaginal administration. Each 2 g vaginal suppository contains 5 mg of hyaluronic acid sodium salt in a base consisting of a mixture of semi-synthetic glycerides. REVAREE vaginal suppositories carry out its activity thanks to the presence of hyaluronic acid, a mucopolysaccharide which is abundantly distributed in many body tissues. Hyaluronic acid has the capacity of retaining water thereby forming a moist environment that is supportive of hydration and lubrication.

INDICATIONS

INDICATIONS
REVAREE is a personal lubricant, for vaginal application, intended to moisturize and lubricate, to enhance the ease and comfort of intimate sexual activity and supplement the body's natural lubrication. This product is not compatible with natural rubber latex, polyurethane, and polyisoprene condoms.

INSTRUCTIONS FOR USE

INSTRUCTIONS FOR USE
Place the suppository into the vagina, preferably at bedtime.
The frequency with which the product should be used depends on the grade of the vaginal dryness. One vaginal suppository every two or three days for a period of thirty days is suggested, unless otherwise recommended by a health care provider. Avoid excessive handling of the vaginal suppository; it is designed to melt at body temperature.

Figure 1

1. Remove the vaginal suppository from its packaging by pulling on the two pre-cut flyers of the plastic strip (as shown in Figure 1).
2. Holding the suppository with your thumb and a finger, insert it into the vagina.
3. Using your finger, gently push the suppository into the vagina as far as it will comfortably go. This should be done while lying on your back with your knees bent.
4. Once inside the vagina, the suppository melts. Lie down as soon as possible. This will keep leakage to a minimum.

INGREDIENTS

INGREDIENTS Hyaluronic acid sodium salt 5 mg., semi-synthetic glycerides.

19c Estrace Package Insert

<https://www.allergan.com/assets/pdf/estrace.pdf>

19d Data Tracking Sheet Sample

19e Patient Consent Form
Attached separately

CONFIDENTIAL

This material is the property of the NYU School of Medicine and Langone Medical Center. Do not disclose or use except as authorized in writing by the study sponsor.

Interventional Template Version: 11 January 2019

19f Patient Key Information
Attached separately

19g Female Sexual Function Index

Appendix 1. Female Sexual Function Index Scoring

Question	Response Options
1. Over the past 4 weeks, how often did you feel sexual desire or interest?	5 = Almost always or always 4 = Most times (more than half the time) 3 = Sometimes (about half the time) 2 = A few times (less than half the time) 1 = Almost never or never
2. Over the past 4 weeks, how would you rate your level (degree) of sexual desire or interest?	5 = Very high 4 = High 3 = Moderate 2 = Low 1 = Very low or none at all
3. Over the past 4 weeks, how often did you feel sexually aroused ("turned on") during sexual activity or intercourse?	0 = No sexual activity 5 = Almost always or always 4 = Most times (more than half the time) 3 = Sometimes (about half the time) 2 = A few times (less than half the time) 1 = Almost never or never
4. Over the past 4 weeks, how would you rate your level of sexual arousal ("turn on") during sexual activity or intercourse?	0 = No sexual activity 5 = Very high 4 = High 3 = Moderate 2 = Low 1 = Very low or none at all
5. Over the past 4 weeks, how confident were you about becoming sexually aroused during sexual activity or intercourse?	0 = No sexual activity 5 = Very high confidence 4 = High confidence 3 = Moderate confidence 2 = Low confidence 1 = Very low or no confidence
6. Over the past 4 weeks, how often have you been satisfied with your arousal (excitement) during sexual activity or intercourse?	0 = No sexual activity 5 = Almost always or always 4 = Most times (more than half the time) 3 = Sometimes (about half the time) 2 = A few times (less than half the time) 1 = Almost never or never

CONFIDENTIAL

This material is the property of the NYU School of Medicine and Langone Medical Center. Do not disclose or use except as authorized in writing by the study sponsor
Interventional Template Version: 11 January 2019

7. Over the past 4 weeks, how **often** did you become lubricated ("wet") during sexual activity or intercourse?

0 = No sexual activity
5 = Almost always or always
4 = Most times (more than half the time)
3 = Sometimes (about half the time)
2 = A few times (less than half the time)
1 = Almost never or never

8. Over the past 4 weeks, how **difficult** was it to become lubricated ("wet") during sexual activity or intercourse?

0 = No sexual activity
1 = Extremely difficult or impossible
2 = Very difficult
3 = Difficult
4 = Slightly difficult
5 = Not difficult

9. Over the past 4 weeks, how often did you **maintain** your lubrication ("wetness") until completion of sexual activity or intercourse?

0 = No sexual activity
5 = Almost always or always
4 = Most times (more than half the time)
3 = Sometimes (about half the time)
2 = A few times (less than half the time)
1 = Almost never or never

10. Over the past 4 weeks, how **difficult** was it to maintain your lubrication ("wetness") until completion of sexual activity or intercourse?

0 = No sexual activity
1 = Extremely difficult or impossible
2 = Very difficult
3 = Difficult
4 = Slightly difficult
5 = Not difficult

11. Over the past 4 weeks, when you had sexual stimulation or intercourse, how **often** did you reach orgasm (climax)?

0 = No sexual activity
5 = Almost always or always
4 = Most times (more than half the time)
3 = Sometimes (about half the time)
2 = A few times (less than half the time)
1 = Almost never or never

12. Over the past 4 weeks, when you had sexual stimulation or intercourse, how **difficult** was it for you to reach orgasm (climax)?

0 = No sexual activity
1 = Extremely difficult or impossible
2 = Very difficult
3 = Difficult
4 = Slightly difficult
5 = Not difficult

13. Over the past 4 weeks, how **satisfied** were you with your ability to reach orgasm (climax) during sexual activity or intercourse?

0 = No sexual activity
5 = Very satisfied
4 = Moderately satisfied
3 = About equally satisfied and dissatisfied
2 = Moderately dissatisfied
1 = Very dissatisfied

14. Over the past 4 weeks, how **satisfied** have you been with the amount of emotional closeness during sexual activity between you and your partner?

0 = No sexual activity
5 = Very satisfied
4 = Moderately satisfied
3 = About equally satisfied and dissatisfied
2 = Moderately dissatisfied
1 = Very dissatisfied

15. Over the past 4 weeks, how **satisfied** have you been with your sexual relationship with your partner?

5 = Very satisfied
4 = Moderately satisfied
3 = About equally satisfied and dissatisfied
2 = Moderately dissatisfied
1 = Very dissatisfied

16. Over the past 4 weeks, how **satisfied** have you been with your overall sexual life?

5 = Very satisfied
4 = Moderately satisfied
3 = About equally satisfied and dissatisfied
2 = Moderately dissatisfied
1 = Very dissatisfied

17. Over the past 4 weeks, how **often** did you experience discomfort or pain during vaginal penetration?

0 = Did not attempt intercourse
1 = Almost always or always
2 = Most times (more than half the time)
3 = Sometimes (about half the time)
4 = A few times (less than half the time)
5 = Almost never or never

18. Over the past 4 weeks, how **often** did you experience discomfort or pain following vaginal penetration?

0 = Did not attempt intercourse
1 = Almost always or always
2 = Most times (more than half the time)
3 = Sometimes (about half the time)
4 = A few times (less than half the time)
5 = Almost never or never

19. Over the past 4 weeks, how would you rate your **level** (degree) of discomfort or pain during or following vaginal penetration?

0 = Did not attempt intercourse
1 = Very high
2 = High
3 = Moderate
4 = Low
5 = Very low or none at all

CONFIDENTIAL

19h Vaginal Symptom Index

Vaginal Symptom Index Score

1. Vaginal dryness

0=none
1=mild
2=moderate
3=severe

2. Vaginal soreness

0=none
1=mild
2=moderate
3=severe

3. Vaginal irritation

0=none
1=mild
2=moderate
3=severe

4. Vaginal discharge

0=none
1=mild
2=moderate
3=severe

5. Dyspareunia

0=none
1=mild
2=moderate
3=severe

19i Patient Global Impression of Improvement

Check the number that best describes how your post-intervention condition is now, compared with how it was before the intervention:

Very much better = 1

Much better = 2

A little better = 3

No change = 4

A little worse = 5

Much worse = 6

Very much worse = 7

CONFIDENTIAL

This material is the property of the NYU School of Medicine and Langone Medical Center. Do not disclose or use except as authorized in writing by the study sponsor
Interventional Template Version: 11 January 2019

20 Schedule of Events

Activity	Visit 1 (Day 0)	Visit 2 (12 weeks +/- 1 week)
Study team procedures		
Routine history of present illness, medical, obstetrical, gynecological, surgical, medication, HRT usage history	X	
Vitals and routine physical exam including pelvic	X	X
GSM Diagnosis	X	
Consent	X	
VAS score for dyspareunia, itching, and dryness	X	X
Rugal fold presence	X	X
VSQ, FSI, VSI	X	X
Randomization	X	
Study drug/device dispensation	X	
Participant study drug/device compliance check		X
Check for side-effects and/or AE due to study agent		X
Laboratory Assessments		
Urine pregnancy test	X	
Urine analysis	X	
Vaginal pH	X	X
VMI	X	X

CONFIDENTIAL

This material is the property of the NYU School of Medicine and Langone Medical Center. Do not disclose or use except as authorized in writing by the study sponsor
Interventional Template Version: 11 January 2019

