7.2.3 Enrollment/Baseline

Screening/Enrollment/Baseline Visit (Visit 1, Day 0)

- Obtain informed consent of potential participant verified by signature on study informed consent form
- Obtain demographic information, history of present illness, medical history, surgical history, obstetrical history, gynecologic history, medication history, HRT usage history
- Perform physical exam: vitals, cardiovascular, abdominal, pelvic
- Diagnose GSM
- If GSM diagnosis, explain study and verify inclusion and exclusion criteria
- Obtain urine pregnancy test: result must be negative and available prior to administration of study agents

CONFIDENTIAL

This material is the property of the NYU School of Medicine and Langone Medical Center. Do not disclose or use except as authorized in writing by the study sponsor
Interventional Template Version: 11 January 2019

- Obtain urine analysis: result must be negative and available prior to administration of study agents
- Record VAS scores for dyspareunia, itching, and dryness
- Record rugal fold analysis
- Collect pelvic samples for vaginal pH and vaginal tissue scraping for VMI
- Have patient fill out VSQ, FSFI, VSI
- Perform randomization and determine patient study arm
- Give patient appropriate prescription (HLA vs vaginal estrogen)
- Counsel on medication dosage, usage, and application
- Counsel on communication routes to inform research team about side effects and/or AE

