7.2.4 Final Study Visit

Final Study Visit (Visit 2, Week 12 +/- 3 to 5 days)

- Record AE as reported by participant or observed by investigator
- Record participant's adherence to treatment regimen
- Record VAS scores for dyspareunia, itching, and dryness
- Record vital signs, results of physical exam including pelvic
- Collect pelvic samples for vaginal pH and vaginal tissue scraping for VMI
- Have patient fill out VSQ, FSFI, VSI, PGI-I
- Discuss the preliminary changes in their symptoms, if any exist
- Provide contact information for [name] to communicate any AE or side-effect experienced after the end of the study if patient believes it is related to the study

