8.3 Time Period and Frequency for Event Assessment and Follow-Up

The occurrence of an AE or SAE may come to the attention of study personnel during study visits and interviews of a study participant presenting for medical care, or upon review by a study monitor. All AEs including local and systemic reactions not meeting the criteria for SAEs will be captured on the appropriate RF. Information to be collected includes event description, time of onset, clinician's assessment of severity, relationship to study product (assessed only by those with the training and authority to make a diagnosis), and time of resolution/stabilization of the event. All AEs occurring while on study must be documented appropriately regardless of relationship. All AEs will be followed to adequate resolution.

Any medical condition that is present at the time that the participant is screened will be considered as baseline and not reported as an AE. However, if the study participant's condition deteriorates at any time during the study, it will be recorded as an AE. UPs will be recorded in the data collection system throughout the study.

Changes in the severity of an AE will be documented to allow an assessment of the duration of the event at each level of severity to be performed. AEs characterized as intermittent require documentation of onset and duration of each episode.

The PI will record all reportable events with start dates occurring any time after informed consent is obtained until 7 (for non-serious AEs) or 30 days (for SAEs) after the last day of study participation. At each study visit, the investigator will inquire about the occurrence of AE/SAEs since the last visit. Events will be followed for outcome information until resolution or stabilization.

CONFIDENTIAL

This material is the property of the NYU School of Medicine and Langone Medical Center. Do not disclose or use except as authorized in writing by the study sponsor
Interventional Template Version: 11 January 2019

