8.4 Reporting Procedures – Notifying the IRB

8.4.1 Adverse Event Reporting

The patient will be given [name], [name], and [name] contact to report any AE. AE's deemed to be related to the study will be reported to the IRB within 7 days of the investigator becoming aware of the event. [name], the principal investigator, will be responsible for completing and signing off on AE reports.

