10.4.5.1 Safety Review

There are no anticipated side-effects to the investigational agent. The control agent is FDA approved for the condition being studied in this trial. Thus, study enrollment will only be stopped if unforeseeable, significant side effects or life-threatening adverse events occur in either study cohort. No statistical rules will be used to halt enrollment due to the short duration of the study and lack of interim analysis.

Patients will be counseled at the start of the study to call [name] or [name] for any side-effect or AE they believe is related to study medication usage. Otherwise, after the baseline visit, the next formal visit will be the final visit at week 12 when medication safety questions will be asked.

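### The Section 20 adverse event row and the 10.4.5.1 counselling sentence are worded as related-only and conflict with Sections 8.3, 7.2.4, 7.2.5, 8.4.1 and 8.4.2

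*Combined protocol and SAP*

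**What the plan says.** Two places limit AEs by presumed cause.

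- Section 20, Schedule of Events, has one AE row, marked at Visit 2 only: "Check for side-effects and/or AE due to study agent".
- Section 10.4.5.1 says participants will be counselled to call "for any side-effect or AE they believe is related to study medication usage". It adds that after baseline "the next formal visit will be the final visit at week 12 when medication safety questions will be asked".

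Several places set no such limit.

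- Section 8.3: "All AEs occurring while on study must be documented appropriately regardless of relationship". Also: "At each study visit, the investigator will inquire about the occurrence of AE/SAEs since the last visit".
- Section 7.2.4, final visit: "Record AE as reported by participant or observed by investigator". Section 7.2.5 repeats this for both early-termination branches.
- Section 7.2.3, baseline visit: "Counsel on communication routes to inform research team about side effects and/or AE".
- Section 8.4.1 gives participants a "contact to report any AE", and Section 8.4.2 does the same for any serious AE.

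The AE definition in Section 8.1.1 has no causal element. Section 8.2.2 has the examining clinician grade causality for events that have already been collected.

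**The concern.** Causality should be judged after an event is recorded, by someone qualified to judge it. The Section 20 row reverses that order for staff. The 10.4.5.1 sentence reverses it for participants and hands them the judgement. An event dropped at that stage never reaches clinician grading (8.2.2), the six-month AE review (8.7) or the safety tables (10.4.3), and it cannot be recovered at analysis.

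Three features of this trial make the wording matter.

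- There is one planned post-baseline visit. Until then, what the site learns depends largely on participants coming forward.
- Reporting of serious AEs to the sponsor under Section 8.5 is required whatever the relationship, but the 24-hour and 72-hour limits run from site awareness. A participant hospitalised for something she thinks unrelated has no reason to call under 10.4.5.1, so the site may first hear of it at week 12.
- The trial is open label, and the stated expectations differ by arm. Section 10.4.5.1 anticipates no side effects from HLA, while Section 2.4.1 lists many reactions to vaginal estrogen. Attribution could therefore differ by arm.

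**Working it through.** The plan states no figure on this point, so there is nothing to reproduce. The check is to compare every instruction on how AEs are found.

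| Place | Who acts on it | Relatedness test before recording? |
|---|---|---|
| Section 20 row, Visit 2 | Staff at the visit | Yes |
| 10.4.5.1 counselling | Participant, between visits | Yes, by her own belief |
| 7.2.3 counselling item | Staff and participant, baseline | No |
| 7.2.4 final visit | Staff | No |
| 7.2.5 early termination, both branches | Staff | No |
| 8.3 documentation and visit inquiry | Investigator | No |
| 8.4.1 and 8.4.2 contacts | Participant | No |
| 7.2.6 unscheduled visit | Staff | No |
| 5.7.2 calls after withdrawal | Staff | No |

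**Step 1.** The conflict is direct. At Visit 2, Section 20 asks about events due to the agent, while 7.2.4 and 8.3 ask about events without that limit. Between visits, 10.4.5.1 tells the participant to call about events she thinks related, while 8.4.1 and 8.4.2 give her a contact for any event.

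**Step 2.** The two narrow passages are the outliers. Elsewhere, a belief test for what participants report applies only after the last visit (end of 7.2.4; 8.3 on later events). The restriction to related events in 8.4.1 and 8.4.2 governs expedited reporting to the IRB, not collection, so it neither supports nor weakens the point. Section 10.4.3 describes the source of the tabulated AEs too unclearly to settle the matter.

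**Step 3.** Can the effect be sized? Let p be the true risk of an AE, equal in both arms, and q the probability that an AE is recorded. With 30 per arm (Section 10.5), expected participants with a recorded AE = 30 × p × q, and the apparent risk difference = p × (q for HLA − q for estrogen). The documents give neither p nor q, so all values below are assumptions.

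| q, HLA v estrogen | p = 0.10 | p = 0.20 | p = 0.30 | Apparent difference, HLA − estrogen (points) |
|---|---|---|---|---|
| 1 v 1 | 3.0 v 3.0 | 6.0 v 6.0 | 9.0 v 9.0 | 0, 0, 0 |
| 0.8 v 0.8 | 2.4 v 2.4 | 4.8 v 4.8 | 7.2 v 7.2 | 0, 0, 0 |
| 0.5 v 0.8 | 1.5 v 2.4 | 3.0 v 4.8 | 4.5 v 7.2 | −3, −6, −9 |
| 0.3 v 0.8 | 0.9 v 2.4 | 1.8 v 4.8 | 2.7 v 7.2 | −5, −10, −15 |
| 0.8 v 0.5 | 2.4 v 1.5 | 4.8 v 3.0 | 7.2 v 4.5 | +3, +6, +9 |

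With equal q below 1, both rates are understated (by 20% at q = 0.8) and the difference stays at zero. With unequal q, the sign follows whichever arm is filtered more. The result is set entirely by the assumed q. An unrestricted question at week 12 would raise q by recovering events that were not phoned in. The table therefore shows only that an effect is possible in either direction.

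**The case against.** The strongest reply is that the design is already right and only two phrases are loose. Sections 7.2.4 and 7.2.5 give the detailed visit procedure without a filter, 8.3 requires active inquiry at each visit, and the Section 20 row is a short label for that procedure. Counselling in 7.2.3 and the contacts in 8.4.1 and 8.4.2 are not limited to related events. Safety is analysed by summary statistics, and Section 10.1 says formal comparisons are not the focus of this pilot. For the halting rule in 8.6 to miss an event, the participant must think it unrelated, the clinician would have had to grade it probably related, and the week-12 inquiry must also fail.

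Much of this stands, and it rules out stronger readings that a reader might infer.

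- *The plan collects only related AEs.* It does not: the passages without a filter outnumber the two with one.
- *A phone call is the only route before week 12.* It is not. Section 7.2.6 provides unscheduled visits, 8.3 allows for events that surface when a participant seeks care or on monitor review, and 5.7.2 provides contact after withdrawal.
- *The wording favours HLA in the AE comparison.* The documents give no attribution rates, and nothing shows that participants are told the 10.4.5.1 expectation about HLA.

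What does not stand is that correct text elsewhere makes the narrow text harmless. A schedule commonly serves as the visit checklist, and 10.4.5.1 is the most explicit statement of which events participants are told to report. Staff and participants hold two incompatible instructions, and the plan does not say which governs.

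**Conclusion.** The conflict holds and rests on the text alone. The Section 20 row and the 10.4.5.1 counselling sentence are related-only and cannot be squared with 8.3, 7.2.4, 7.2.5, 8.4.1 and 8.4.2. If staff follow the schedule row, or participants follow the 10.4.5.1 counselling, events judged unrelated could be under-reported or reported late before a clinician has assessed them. With open-label treatment and one planned post-baseline visit, this could differ by arm. That is a risk, conditional on which instruction is followed; it is not an established bias. No size or direction can be given, because the documents contain no AE risk and no attribution rate. The wording should be corrected because the change is small and an event never elicited is lost. The primary endpoint and the sample size are not affected.

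**What to change.** Make two wording changes so that the plan agrees with Section 8.3.

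1. Section 20: replace the AE row with *Record all AEs since last visit, regardless of relationship*.
2. Section 10.4.5.1: have participants counselled to call about *any new or worsening symptom or illness*, dropping the test of what they believe is related.

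State that the same question is put to both arms and that the clinician grades causality afterwards under Section 8.2.2.

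The cost is slightly more AE recording. No visit, procedure, endpoint or participant number changes.
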